9.3 Analysis Supporting Secondary Objective(s)

Secondary objectives are:

Safety of the patient, efficacy of the procedure, MRI image description and patient satisfaction.

Patient safety will be analyzing the number of AE, SAE and SUSARs and will be compared for both groups. The numbers obtained will be compared in a Chi-Square test. SUSARs will only occur, if any, in the operated group and thus cannot be compared to any other value. For categorial variables. Efficacy of the procedure will be analyzed by counting the number of failed procedures in the operated group. Because this value will only be determined in the operated group, there is no statistical analysis. The efficacy of the procedure must be over 80%. If the failed procedures are higher than 20 % the benefit-risk balance will be re-evaluated. The MRI signal will be evaluated after a modified scheme of Genovese [32]. The size of the meniscus and the amount of extrusion of the meniscus will be measured and recorded in both groups. The obtained numbers will be compared to the other group at the same time point and to the value before surgery/at the beginning of the trial. This will be performed with an unpaired t-Test if the values are normally distributed or with the Mann-Whitney-U-test for not normally distributed values. Patient satisfaction is a categorial value and will be only evaluated in the operated group. The number of patients who are very pleased, pleased, not pleased, very unsatisfied will be described by means of frequency tables and plots.

Intercurrent event are: progression of osteoarthritis up to TKA, lost to follow-up, premature death, the patient wishes to change to the operated group after a certain time. If these events happen, the data will be available until the event. Last date recorded will be analyzed. Progression of osteoarthritis up to TKA will be recorded as fail and will be reported as this. Patients changing to the operated group will be analyzed up to the date of change in the non-operated group. Missing data will not be estimated. A drop-out rate (lost to follow-up, premature death) of 20% is expected and accepted.

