8.4.2 Time Period and Frequency for Collecting AE and SAE Information

At each follow-up (at the end of the hospital stay, after 6 weeks, after 6, 12 and 24 months and after 5 years, for the operated group and after 6, 12, 24 months and 5 years for the non-operated group) AE and SAE are collected regularly. Since the patient can inform the investigator about AE, or SAE at any time, collecting AE and SAE are performed as soon as known by the investigator. After finishing the trial, the investigator is still reachable for the patient to inform him about any AE or SAE.

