9.1 Analysis Sets

Full analysis set will be performed.

PROMs:

Change from baseline for the PROMs (IKDC, KOOS, VAS-pain score) for the operated/non-operated group after 6, 12 and 24 months and 5 years and between groups.

Complications, AE, SAE and SUSARs:

The number of complications, AE, SAE and SUSARs will be evaluated at each time point and compared between the groups with Fishers exact test.

MRI evaluation:

Change in MRI evaluated using the Outerbridge [1] graduation, the size of the meniscal defect and the meniscus itself, the MRI signal of the meniscus will be evaluated after a modified score after Genovese et al.[32] and the number of patients with an extrusion and the size of the extrusion.

Patient satisfaction:

Patient satisfaction will be categorized as: very pleased, pleased, not pleased, very unsatisfied and will be evaluated using the Chi-square test.

Progression of osteoarthritis up to TKA:

The number of patients with progression of osteoarthritis up to TKA for both groups will be compared with a Kaplan-Meier time to event curve.

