9.5 Safety Analyses

Patient safety will be analyzed by recording AE, SAE and SUSARs. The number of these events will be recorded and compared for both groups. SUSARs will only occur, if any, in the operated group. The frequencies obtained will be displayed in bar plots and tables with group comparisons based on Fisher's exact test. Safety is a secondary outcome and is described in detail in 9.3.

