12 APPENDIX: ADVERSE EVENTS AND SERIOUS ADVERSE EVENTS – DEFINITIONS, SEVERITY, AND CAUSALITY

12.1 Further Details and Clarifications on the AE Definition

There are no regional AE requirements. An adverse event log is filled to follow the adverse event until it is solved.

A trial related adverse event is redness, haematoma, swelling, infection of the operated site and pain of the treated knee. This will be recorded in the electronic patient chart and in the CRF.

Progression of osteoarthritis up to TKA does not meet AE definition; it is the normal progression of the disease and will be expected to be more observed in the non-operated group.

The IMP of this clinical trial is human cancellous bone, there is no dose, there are only dimensions of the transplant. Thus, there is no overdose.

Lack of efficacy of the procedure is provided when more than 20% of the procedures fail.

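### The between-group safety comparison is assigned two different tests, counts events instead of patients, and is contradictory on whether SUSARs are compared at all

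*Protocol*

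**What the plan says.** Three sections of the Protocol describe the same comparison.

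- **9.1 Analysis Sets:** "The number of complications, AE, SAE and SUSARs will be evaluated at each time point and compared between the groups with Fishers exact test".
- **9.3 Analysis Supporting Secondary Objective(s):** "Patient safety will be analyzing the number of AE, SAE and SUSARs and will be compared for both groups". It continues: "The numbers obtained will be compared in a Chi-Square test". It then says that SUSARs can arise only in operated patients and so have nothing to be compared with.
- **9.5 Safety Analyses:** "The number of these events will be recorded and compared for both groups", displayed "with group comparisons based on Fisher's exact test". It ends: "Safety is a secondary outcome and is described in detail in 9.3".

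Other sections bear on what is being compared. Section 3.2 makes treatment-related AEs and SAEs the safety endpoint. Section 12.1 lists the trial-related events: "A trial related adverse event is redness, haematoma, swelling, infection of the operated site and pain of the treated knee". Section 6.1 gives the IMP and NIMP to the surgical group only. Section 8.4.1 defines an AE as arising in a subject who has been given a medicinal product, yet 8.4.2 collects AEs and SAEs in both groups. Its schedule is "at the end of the hospital stay, after 6 weeks, after 6, 12 and 24 months and after 5 years, for the operated group"; for the non-operated group it is 6, 12 and 24 months and 5 years. Sections 8.4.2 and 8.4.3 add that events are also taken up whenever the investigator learns of them.

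**The concern.** There are three separate faults.

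1. **Two tests.** The protocol does not leave the test open for later. It fixes it three times, in two ways, and the section naming Fisher's test defers to the section naming chi-square. The investigator is also the sponsor, sees the outcome data during the trial and performs the analysis (9.7, 10.4), so an unresolved choice of test should not remain.
2. **Wrong unit.** Each section speaks of the number of events. The local reactions in 12.1 can easily occur together in one knee, so events cluster within patients. A contingency-table test needs independent units, and patients are those units.
3. **Comparison without a counterpart.** Section 9.1 puts SUSARs into the between-group test and 9.3 says this cannot be done. The treatment-related events of 3.2 have the same difficulty, because controls receive neither IMP nor NIMP.

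At stake is whether a published safety p-value can be interpreted, in a trial that 4.1 says is meant to prove patient safety.

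**Working it through.** The Protocol states no figure for the safety comparison, so there is nothing to reproduce.

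**Inputs.** Group sizes are 30 and 10 (9.7), or 24 and 8 after 20% loss (9.8). The 0.05 level is stated in 9.2 for the PROMs and is assumed here for safety. No AE rate is given; a range of 5% to 50% of patients is assumed.

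**Step 1: expected counts.** If m patients in total have an event, the smallest expected cells are those of the control group.
- At 30/10 they are 10m/40 = m/4 and (40 − m)/4. Both reach 5 only if m ≥ 20 and m ≤ 20, that is m = 20.
- At 24/8 they are m/4 and (32 − m)/4. Both reach 5 only if m ≥ 20 and m ≤ 12, which is impossible.

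**Step 2: does the choice of test change the result?** For a 2×2 table with rows (a, b) and (c, d), the uncorrected statistic is N(ad − bc)² divided by the product of the four margins.
- 9/30 vs 0/10: 40 × (9 × 10 − 21 × 0)² / (30 × 10 × 9 × 31) = 324,000 / 83,700 = 3.87, p = 0.049. Fisher p = 0.081.
- 0/30 vs 2/10: 40 × (0 × 8 − 30 × 2)² / (30 × 10 × 2 × 38) = 144,000 / 22,800 = 6.32, p = 0.012. Fisher p = 45/780 = 0.058.

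There are 31 × 11 = 341 possible tables at 30/10. The uncorrected chi-square and Fisher's test disagree at 0.05 in 20 of them (20/341 = 5.9%). In all 20 the chi-square is the one below 0.05.

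**Step 3: type I error at 30/10, on patients with at least one event, equal rates of 5% to 50%.**

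| Test | Type I error |
|---|---|
| Uncorrected chi-square | 0.023 to 0.054 |
| Fisher's exact | 0.007 to 0.028 |

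The probability that the two tests disagree is 0.012 to 0.030 over the same range.

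**Step 4: effect of counting events.** Suppose 30% of patients in both groups are affected, each with 1 plus a Poisson number of further events. Event totals are compared with the 3:1 split by chi-square at 0.05, in 20,000 simulated trials.

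| Mean events per affected patient | Type I error |
|---|---|
| 1 | about 0.02 |
| 2 | about 0.16 |
| 3 | about 0.24 |

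**Step 5: events possible only after surgery.** The table is x/30 vs 0/10. Fisher gives p = 1.0 at x = 1 and x = 2, and first falls below 0.05 at x = 10 (p = 0.043). The control zero is fixed in advance, so the p-value carries no comparative information.

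**Step 6: what the operated group alone can show.** The exact (Clopper-Pearson) upper 95% limit for 0/30 is 1 − 0.025^(1/30) = 11.6%; for 1/30 it is 17.2%.

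**The case against.** The strongest reply is that little turns on this. Safety is secondary. The stopping provisions in 7.4 and 9.7 rest on a benefit-risk re-evaluation and a 20% failure rate, not on a safety p-value. The counting unit is often left to a statistical analysis plan, and frequencies tested with Fisher's test in 9.5 could be read as patient counts. The point about low consequence stands and limits the weight of the finding. The point about the unit stands only in part: patient counts are a possible reading, but no section says so and all three say numbers of events.

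Four stronger readings might be inferred and are not supported.

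- **That the two tests generally give opposite answers.** They do so in 20 of 341 tables, and only one of those has no control events (9/30 vs 0/10). Both worked examples use the uncorrected chi-square. With continuity correction, p = 0.126 and 0.094, on the same side of 0.05 as Fisher; the corrected version disagrees with Fisher in 8 other tables. The Protocol does not say which version is meant.
- **That the whole comparison tests events controls cannot have.** Section 9.3 itself exempts SUSARs, 8.4.2 collects AEs and SAEs in controls, and 11.1 accepts that these may be unrelated to the IMP. An all-cause comparison is a legitimate reading.
- **That unequal visits make the comparison void.** Controls have no discharge or 6-week visit, but events are also recorded whenever they become known.
- **That the comparison should therefore start at 6 months.** Section 8.3 places the highest safety risk during surgery. Dropping that period would favour the operated group by construction.

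**Conclusion.** The concern holds in three parts, all visible in the text: two tests for one comparison with a cross-reference that deepens the conflict; events used as the unit; and 9.1 contradicting 9.3 on SUSARs, a difficulty shared by the treatment-related endpoint in 3.2.

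The choice of test is a modest matter numerically, affecting 1% to 3% of trials under equal event rates. The unit matters more: type I error could reach about 0.16 to 0.24 where affected patients average two or three events. Those last figures depend on the assumed 30% affected, the assumed clustering and the 0.05 level, none of which the Protocol gives for safety. The expected-count result depends only on the stated group sizes.

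This should be corrected before analysis, but it does not touch the primary endpoint or any stated power or sample size.

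**What to change.** 1. Delete the chi-square sentence for safety in 9.3 and name Fisher's exact test in 9.1, 9.3 and 9.5.
2. Define the unit as patients with at least one event, separately for all-cause AEs and all-cause SAEs.
3. Remove SUSARs from the Fisher sentence in 9.1, in agreement with 9.3.
4. Report treatment-related AEs, treatment-related SAEs and SUSARs descriptively in the operated group, as patient proportions with exact 95% confidence intervals.
5. Keep the whole follow-up, including the perioperative period, in the all-cause comparison, and note beside it that controls have no discharge or 6-week visit.

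The cost is wording only; no additional data are needed. The one statistical price is that Fisher's test is conservative at 30/10, so it will miss some differences that a chi-square would flag.

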1.3 Schedule of Activities

Observation parameter in detail:

| Parameter | Screening (EU*) | Enrollment? yes/no | Surgery OP | Follow-up | | | | | |
|---|--------------------|-----------------------|---------------|-----------------|----|----|----|----|----|
| | | | | U1 [#] | U2 | U3 | U4 | U5 | U6 |
| date | V | | V | V | V | V | V | V | V |
| surgeon | V | | V | V | V | V | V | V | V |
| Medical history (age, gender, working status, co-morbidities) | V | | | | | | | | |
| weight | V | | | | | | | | V |
| height | V | | | | | | | | V |
| BMI | V | | | | | | | | V |
| Nicotine | V | | | | | | | | V |
| Side | V | | | | | | | | |
| Previous knee treatment | V | | | | | | | | |
| Cartilage damage | V | | | | | | | | |
| Leg axis misalignment | V | | | | | | | | |
| Properties of the meniscus | V | | | | | | | | |
| Sport | V | | | | | | V | V | V |
| Scores (KOOS, IKDC) | V | | | | | | V | V | V |
| VAS-pain Score | V | | | | | | V | V | V |
| Diagnose | V | | | | | | | | |
| Inclusion criteria | V | V | | | | | | | |
| Exclusion criteria | V | V | | | | | | | |
| Written informed consent | | V | V | V | V | V | V | V | V |
| Pregnancy test | | | V | | | | | | |
| Surgeon | | | V | | | | | | |
| Time of surgery | | | V | | | | | | |
| Graduation after Outerbridge [1] | | | V | | | | | | |
| Way of Fixation | | | V | | | | | | |
| Spongioflex®-properties | | | V | | | | | | |
| Antibiotica | | | V | | | | | | |
| Additional Procedures | | | V | | | | | | |
| Complication | | | V | V | V | V | V | V | V |
| MR-image evaluation | V | | | | V | V | V | V | V |
| Pain at rest | | | | V | V | V | V | V | V |
| Pain when walking | | | | V | V | V | V | V | V |
| Pain at sport | | | | | V | V | V | V | V |
| Pain medication | V | | | V | V | V | V | V | V |
| Reoperation | | | | V | V | V | V | V | V |
| Patient satisfaction | | | | | V | V | V | V | V |

*EU: screening visit; U1: at the end of hospital stay; U2: 6 weeks after surgery (\pm 4 days); U3: 6 months after surgery (\pm 1 months); U4: 12 months after surgery (\pm 1 months), U5: 24 months after surgery (\pm 1 months); U6: 5 years after surgery (\pm 3 months); [#]grey shading: this parameter will only be evaluated when operated

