9.2.1 Statistical Model, Hypothesis, and Method of Analysis

The change in PROMS from baseline in the operated and non-operated group will be compared by two-sided t-test for independent groups when data are normally distributed or with the Mann-Whitney-U-test.

The Null-hypothesis is that partial meniscal replacement does not improve mean PROMs for knee function in comparison to the non-operated group after 2 and 5 years.

The alternative hypothesis is that there that partial meniscal replacement does improve mean PROMs for knee function in comparison to the non-operated group after 2 and 5 years.

The PROMS should improve (Mean KOOS and IKDC should increase by at least 20 points, and VAS-pain score should decrease by at least 3 points, or to near zero, depending on the pre-surgical value).

Analysis of data will be performed by direct comparison of the groups at each time point and in comparison, to before surgery/start of the trial. Mean and standard deviation of the groups are compared. If there is a significant difference, the Null-Hypothesis will be rejected. Even when we have a loss of follow-up of 20% the power will still be 0.985. From our experience mean KOOS values presurgical are between 40-50 and between 50-60 for the IKDC, after treatment the expected improvement is to mean values between 80-90 for both scores. For the VAS-pain-score the presurgical mean value is around 4 and the post-surgical value is between 0 and 1. There is no risk of a type 1 error, because the values are measured several times over the follow-up period, thus there will be no false positive result. If the difference in the scores between pre- and post-surgery is lower than 18, the power is not big enough. Thus setting 20 as the difference for rejecting the Null-hypothesis is supported by enough power, even with only 8/24 patients in the respective group. The covariate could be smoking and sex. Smoking affects healing in general. It is not clear if there will be enough patients in each group to use these as confounders. Interactions will not be possible, because the treatment has no relation to any characteristic of the patient. There will be no adjustment made and no model fitting.

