9.2.4 Sensitivity Analysis

The intercurrent events in this trial are progression of osteoarthritis up to TKA, lost to follow-up, premature death and change to the other treatment group. Progression of osteoarthritis up to TKA will be defined as procedure failure. Lost to follow-up and premature death can be unrelated to knee problems. Both will be defined as lost to follow up. Lost to follow-up will reduce the power of the result. A drop-out of 20 % is acceptable and will not bias the result.

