10 GENERAL CONSIDERATIONS: REGULATORY, ETHICAL, AND TRIAL OVERSIGHT

10.1 Regulatory and Ethical Considerations

The Investigator is also the sponsor. He is responsible for compliance with the below laws and regulations. The clinical trial will be conducted in compliance with the protocol, with the regulation and with the principles of good clinical practice according to Annex I section D 17 (a) CTR 536/2014, the declaration of Helsinki, the Council for International Organisations of Medical Sciences (CIOMS) International Ethical Guidelines, ICH Good Clinical Practice (GCP) Guidelines (the investigator holds the ICH-GCP-certificate). Additionally the German Bundesdatenschutzgesetz (BDSG) and the General Data protection Regulation (regulation (EU)2016/679), GDPR will be followed.

The study will only start after a positive ethic vote is obtained.

The benefit-risk balance is in focus of the trial and will be evaluated when safety issues occur. The efficacy of the procedure is also in focus and only when the efficacy is over 80% the ethical balance is given.

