11 GENERAL CONSIDERATIONS: RISK MANAGEMENT AND QUALITY ASSURANCE

11.1 Quality Tolerance Limits

Quality tolerance limits are defined in the inclusion/exclusion criteria. The main criteria which may lead to exclusion of the patient from the trial are age (must be over 18 years and under 60 years) and BMI (must be $<30 \text{ kg/m}^2$). The investigator expects a 20% drop in total. If the drop-out will be higher, this could significantly impact the study results. Protocol deviations and violations will not occur, because the surgery is performed after a standardized procedure. The patient does not have any impact on this procedure.

The percentage of withdrawal will be small, because the burden of the trial is very low (filling the 3 questionnaires at the follow-up-visit). The investigator predicts a maximum of 5 % withdrawal, which is included in the 20% mentioned above.

Incomplete data will occur due to lost to follow-up, withdrawal or due to progression of osteoarthritis up to TKA. Progression of osteoarthritis is a very slow process; thus a 2.5% possibility would be defined by the investigator for incomplete data related to progression of osteoarthritis up to TK.

AE and SAE occur at any time and may be not related to the IMP used. SAE not related to the investigational product do not impact study results. SADR/SUSAR's do impact study results. Because human allogeneic cortical bone (in any supply form) was transplanted in different forms several thousand-fold, the manufacturer (DIZG gGmbH, Berlin, Germany) did not receive any information about and SADR or SUSAR up to now.

The IMP is not a pharmacological drug and the administration is not over the trial period. The IMP will be implanted during surgery and remains in the body. It has no systemic effect and it is not a medical device.

Patient follow-up will be the same for patients included in the trial or not, thus the lost to follow-up will be below 10 %, because the follow-up-visits are only a minimal burden.

For ethical reasons, there is no randomization in the trial. The patient decides, if he will be operated, or not. Even if the patient will decide not to be operated in the first round, they have the possibility to change to the surgery group at any time. Thus, there is no pressure on the patient and there is no incorrectly randomized patient.

All this Quality tolerance limits are monitored during the trial via a clinical monitor (CRA).

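### The 80% efficacy criterion is in effect a count of knee replacements, which the protocol itself expects to be rare, so meeting it says almost nothing about whether the implant works

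*Protocol*

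**What the plan says.** Section 3.2 gives the secondary objective on efficacy of the procedure a single endpoint, the number of patients who progress to TKA. Section 9.3 measures it by counting failed procedures in the operated group, without statistical analysis, and adds that "The efficacy of the procedure must be over 80" per cent.

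Section 9.2.4 names the failure event: "Progression of osteoarthritis up to TKA will be defined as procedure failure". Sections 7.1.1, 9.2.2, 9.2.3 and 9.3 say the same in similar terms. One place is wider: the rescue-therapy paragraph under 6.8.2 counts progression to osteoarthritis or to TKA as failed treatment, without giving a grade.

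The threshold is used repeatedly:

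- Section 9.3: "If the failed procedures are higher than 20 % the benefit-risk balance will be re-evaluated". Sections 7.4, 8.2, 9.2.2 and 9.7 contain the same trigger.
- Section 12.1: "Lack of efficacy of the procedure is provided when more than 20% of the procedures fail".
- Section 10.1: "only when the efficacy is over 80% the ethical balance is given".

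On how often TKA is expected, 1.2, 3.1, 3.2 and 4.1 call more than one patient in five years very unlikely. Section 11.1 gives a number: "thus a 2.5% possibility would be defined by the investigator for incomplete data related to progression of osteoarthritis" as far as TKA.

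**The concern.** A success threshold tells the reader something only if an ineffective treatment has a fair chance of missing it. Here the failure event is a late, rare end stage of a disease that the protocol describes as very slow. No lack of gain on the patient-reported outcome measures (PROMs), reoperation, extrusion or poor MRI appearance is declared a failure, although all of these are collected. A patient with unchanged pain and function five years after surgery counts as a success so long as the knee has not been replaced.

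The protocol gives this figure real weight: 10.1 ties the ethical balance to it, and 12.1 uses it to define lack of efficacy. The two-year results are to be published (9.7). A statement there that efficacy exceeded 80% would be read as evidence for the implant, when a low short-term TKA rate alone could produce it.

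**Working it through.** **Inputs.** Operated patients: 30, or 24 after 20% loss (9.8). TKA rate: 2.5% (11.1). Boundaries: efficacy over 80%, failures higher than 20% (both 9.3), success in at least 80% (8.2).

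**The protocol's own rate.** One patient among the 30 + 10 enrolled is 1/40 = 2.5%, which matches 11.1. Expected failures among 30 operated patients are 30 × 0.025 = 0.75.

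**Failures needed.**

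- To miss 'over 80%' with 30 patients: 6, because 24/30 is exactly 80%.
- To exceed 20% failures with 30 patients: 7, because 6/30 is exactly 20%.
- With 24 patients: 5 for either rule, because 20/24 = 83.3% and 19/24 = 79.2%.

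**Probability of reaching each count.** Exact binomial tail, P(X ≥ r) = Σ C(n,k) p^k (1 − p)^(n−k), summed from k = r to n:

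| True TKA rate | 6 or more of 30 | 7 or more of 30 | 5 or more of 24 |
|---|---|---|---|
| 2.5% | 0.000086 | 0.0000075 | 0.00028 |
| 3.3% (1 of 30) | 0.00041 | 0.000047 | 0.0010 |
| 5% | 0.0033 | 0.00057 | 0.0060 |
| 10% | 0.073 | 0.026 | 0.085 |
| 20% | 0.57 | 0.39 | 0.54 |

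At 2.5% the criterion is met with probability above 99.9% under every reading. The 3.3% row covers the case in which the single expected TKA falls in the operated group. For an even chance of more than 20% failures among 30, the true rate would have to be about 22%, nearly nine times the stated figure.

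**The boundary.** Exactly 6 failures of 30 misses 'over 80%' (9.3, 10.1), satisfies 'at least 80%' (8.2), and does not trigger 'higher than 20%' (9.3) or 'more than 20%' (12.1).

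**What a TKA count can show.** With 0 of 30, the exact 95% upper limit is 1 − 0.025^(1/30) = 11.6%. With 0 of 10 it is 1 − 0.025^(1/10) = 30.8%.

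**Why the 80% should not be moved to a responder share.** Section 9.8 expects IKDC 55 to 84 (gain 29) and KOOS 46 to 86 (gain 40). The protocol states no SD of individual change, so I assume normal changes with an SD of 10 to 20. The share gaining at least 20 points is Φ((gain − 20)/SD). For IKDC this is Φ(9/20) = 67% to Φ(9/10) = 82%. For KOOS it is Φ(20/20) = 84% to Φ(20/10) = 98%. On IKDC, 30 patients would then miss 'over 80%' with probability 0.96 (SD 20) to 0.48 (SD 10), even if the expected mean gain is achieved.

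**The case against.** Several points on the other side have force.

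- **Efficacy is tested elsewhere.** The primary objective compares PROM changes with the non-operated group (3.1, 9.2.1), and an implant with no PROM benefit should show itself there. The 80% figure is secondary and descriptive. This stands: a reader might infer that the trial has no meaningful test of efficacy, and the protocol does not support that.
- **Failure is not defined solely as TKA.** The paragraph under 6.8.2 once includes osteoarthritis, and 7.4, 8.2, 9.7, 10.1 and 12.1 state the limit without defining failure. This stands as a reason to reconcile. It does not rescue the criterion, because the wider wording has no grade and the statistical sections consistently name TKA.
- **The 2.5% is not an operated-arm failure rate.** Section 11.1 gives it trial-wide, for incomplete data. This is correct, which is why the table runs to 20%; the conclusion changes little up to 10%.
- **A useless implant is not certain to pass.** Section 12.1 expects more TKA without surgery, and no arm-specific rate is given. A reader might infer a success rate near 100% whatever the implant does; the supportable statement is conditional on TKA staying rare within five years.
- **The operated-only count in 9.3 does not contradict 3.3 and 9.4.** A failed procedure can occur only where a procedure took place, and TKA in both groups is a separate exploratory analysis.
- **The 20-point target is not a per-patient rule.** Section 9.2.1 says "Mean KOOS and IKDC should increase by at least 20 points", so a responder share would be a new measure and must be labelled as one.

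**Conclusion.** The concern holds in limited form. As fixed in 3.2 and 9.3, the secondary efficacy measure is nearly uninformative. At the protocol's 2.5% the chance of missing the criterion is at most 0.00028 across the three counts, and at four times that rate it is 0.026 to 0.085. A result over 80% is what a low TKA rate alone would produce, so it cannot support an efficacy statement, nor can it bear the weight that 10.1 and 12.1 place on it.

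This rests on three assumptions: failure means TKA, as most sections say; patients fail independently; and the true operated-arm rate is of the order the protocol expects. At a true rate near 20% the rule would respond. The inconsistent boundary at 6 of 30, and the different meaning of failure in 6.8.2, are defects whatever the rate.

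**What to change.** In 3.2 and 9.3:

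1. Stop presenting the TKA-only count as efficacy judged against 80%. Report TKA as counts per group with exact 95% confidence intervals.
2. Add a descriptive secondary measure in both groups at 24 months and 5 years: the share of patients whose own change reaches the size that 9.2.1 states as a group mean (20 points on KOOS, 20 on IKDC, 3 points or to near zero on VAS pain). Report it separately for each PROM with an exact 95% interval, and count TKA as non-response. Say that the per-patient use is new, and attach no 80% threshold to it.
3. Reconcile the meaning of a failed procedure (6.8.2 against 9.2.2 to 9.3), and the three boundary wordings, across 7.4, 8.2, 9.2.2, 9.3, 9.7, 10.1 and 12.1. Which definition governs continuation of the trial is for the sponsor to decide.

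The cost is protocol wording. The schedule in 1.3 already collects the PROMs at both time points, and Table 1 in 6.1 has both groups attending those visits. The downside is that the reported success figure will look less favourable than a TKA-only rate.
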